16 patients will be enrolled and treated, starting with the lowest dose, Cohort 1. The first patient in each cohort will be observed for at least 14 days post surgery (through Visit 5) before the rest of the cohort can be enrolled. The safety review committee will review the data prior to clearing the sentinel patient and enrolling the remainder of the cohort. After all 4 patients in a cohort have completed Visit 5, the safety review committee will review available safety data to determine if dose limiting toxicity exists that prohibits enrolling the next higher dose cohort. The respective IRB's will be informed of the outcome of the SRC meetings.

If there are no safety concerns, the next cohort will start treatment.

*Patients may be replaced who do not receive an injection of study medication, or for discontinuing from the study for reasons unrelated to treatment before completing Visit 4.

Page 8 of 52

TABLE OF CONTENTS

CLINICAL RESEARCH PROTOCOL						
Clinical Protocol Approval Form2						
Confidentiality and Investigator Statement						
Study Summary	4					
TABLE OF CONTENTS	8					
Table of Tables	.10					
Table of Figures	.10					
LIST OF ABBREVIATIONS	.11					
1 INTRODUCTION AND RATIONALE	.14					
1.1 Background	.14					
1.2 ONL1204	.14					
1.2.1 Preclinical Experience	.14					
1.2.2 Clinical Experience	.16					
1.3 Study Rationale	.16					
1.3.1 Rationale for the Proposed Doses	.16					
1.3.2 Rationale for Pharmacokinetic testing	.17					
1.3.3 Rationale for Vitreous Tap and Pharmacodynamic Analysis	.17					
1.4 Potential Risks and Benefits	.18					
1.4.1 Potential Risks of Study Product	.18					
1.4.2 Potential Risk to Fetal Development	.18					

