4.1 Overview of Study Design

Sixteen patients will be enrolled in 4 ascending dose groups.

After signing informed consent and meeting all eligibility criteria, patients will undergo a vitreous tap for cytokine and other potential molecular biomarker analysis followed by a single intravitreal injection of ONL1204. This will occur on the day of diagnosis (Day 1). Safety visits will be conducted 1 day post-injection and per Investigator's discretion until Visit 3. At Visit 3 (3+ days post-injection, in accordance with standard of care) patients will undergo surgical repair of their retinal detachment with vitrectomy (with or without scleral buckling) and gas or oil tamponade. At the time of surgery, an undiluted vitreous sample will be collected for pharmacokinetic and pharmacodynamics analyses, and an aqueous sample will be collected for pharmacodynamic analysis. Additional safety visits will be conducted 1 day post-surgery, 14 (+4 days) days post-surgery, Weeks 6, 9 (\pm 7 days each), and Week 24 (\pm 14 days; study exit).

As this is a first-in-human safety study of ONL1204, the first patient in the first cohort will receive the lowest dose of ONL1204. After this patient completes Visit 5 (14 +4 days post-surgery) and a safety review committee reviews the data, the remainder of the patients in that cohort will be enrolled. After all patients in the cohort have completed Visit 5, the SRC will review the available safety data to determine if dose

limiting toxicity exists that prohibits enrolling the next higher dose cohort. This process will be repeated until escalating to the top dose.

The following doses will be evaluated: $25 \ \mu g$, $50 \ \mu g$, $100 \ \mu g$, and $200 \ \mu g$ ONL1204. ONL1204 is available in vials with concentrations of 0.5 mg/mL and 2 mg/mL. Therefore, a volume of 0.05 or 0.1 mL will be injected into the study eye.

Patient participation will be approximately 24 weeks (6 months): a single injection treatment and 24 weeks of follow-up.

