4.2.2 Dose Escalation Decisions

Dose escalation decisions include the following:

- 1. To begin enrolling the next cohort at the planned dose or an adjusted dose.
- 2. To delay opening the next cohort in order to collect additional safety on the current cohort, or to enrol additional patients in the current cohort if safety concerns are identified.
- 3. To stop the cohort escalation if unacceptable toxicities are noted.

If, in the opinion of SRC, dose limiting toxicity is reached, the previous, lower dose will be considered the Maximum Tolerated Dose (MTD).

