9.3.1.7 Systemic PK

The amount of study drug present in the patient plasma will be summarized at each time point. ONL1204 concentrations that are below the quantitation limit (BQL) will be set to 0 if before the first quantifiable concentration and to 0 thereafter for all descriptive analyses of ONL1204. For the calculation of geometric mean and geometric CV%, all BQL values will be set to missing. The number of BQL values at each time point will be summarized through frequency counts and percentages.

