For PK concentration data, the number of non-missing values, number of below limit of quantification (BLQ) values, arithmetic mean, standard deviation, median, minimum, maximum, coefficient of variation (CV%), geometric mean and geometric coefficient of variation (geo CV%) values will be presented. For the calculation of summary statistics, unrounded data will be used and reported to three significant figures except for n, n BLQ, and CV% which will be presented to the nearest integer and one decimal place, respectively.

For PK parameters data, the number of non-missing values, arithmetic mean, standard deviation, median, minimum, and maximum values will be presented. Individual PK parameters will be presented to three significant figures except for T_{max} which will be presented to two decimal places.

- Categorical variables: Descriptive statistics will include counts and percentages per category. The denominator in all percentage calculations will be the number of participants in the relevant analysis population with non-missing data, unless specifically stated otherwise. Percentages will be displayed to one decimal place. Proportions will be displayed to 3 decimal places.
- Unscheduled assessments: Only values collected at scheduled study visits/time points will be presented in summary tables. If a repeat assessment was performed, the result from the original assessment will be presented as the result at the specific visit/time point. All collected data will be included in the data listings.

- Assessment windows: All assessments will be included in the data listings and no visit windows will be applied to exclude assessments that were performed outside of the protocol specified procedure windows.
- Result display convention: Results will be center aligned in all summary tables and listings. Participant identifiers visit and parameter labels may be left-aligned if required.
- Date and time display conventions: The following display conventions will be applied in all outputs where dates and/or times are displayed:

Date only: YYYY-MM-DD

Date and time: YYYY-MM-DD HH:MM

If only partial information is available, unknown components of the date or time will be presented as 'NK' (not known), i.e., '2016-NK-NK'. Times will be reported in military time.

Key Definitions

The following definitions will be used:

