- Actual Time from First Dose (hours) = (Date/Time of First Dose PK Sample collection) (Date/Time of First Dose)
- Actual Time Deviation (hours) = (Actual PK Sample Collection Time Post Dose) (Scheduled PK Sample Collection Time Post Dose).
- Treatment Emergent Adverse Events (TEAEs) are defined as adverse events that occurred following the first administration of study medication.

Inferential Analyses

Descriptive statistics will be used to summarize the safety, PD and PK data. No formal hypothesis testing is planned.

Multiple Comparisons and Multiplicity Adjustments.

Not applicable for this study.

Handling of Missing Data

For the classification of Treatment emergent adverse event (TEAE) and Concomitant medication, the following will be applied in the following order:

- a. If all dates/times (start and stop) missing, the event/medication will automatically be classified as a TEAE/Concomitant medication.
- b. For AEs with a missing start date/time, if the event end date/time is prior to first study drug administration, the event will not be classified as a TEAE.
- c. If only the AE start year/ medication end year is present and is the same or is after the first study drug administration year unit, the event/medication will be classified as a TEAE/Concomitant medication.
- d. If the AE start month and year/medication end month and year are present and are the same or after the first study drug administration month and year units, the event/medication will classified as a TEAE/Concomitant medication.

For plasma concentration-time data/profiles and PK analysis the following will be applied:

- a. Concentrations that are below limit of quantification (BLQ) prior to the dosing (Pre-dose) will be set equal to zero. Post dose BLQ concentrations will be set to zero.
- b. Where there are no results, these will be set to missing.
- c. If more than 75% of values per nominal timepoint and treatment group are BLQ, then all descriptive statistics, except for nBLQ, will be denoted as not calculable (NC).
- d. For the purpose of calculating the non-compartmental plasma PK parameters, concentrations that are BLQ prior to the first quantifiable value will be set equal to zero and BLQ values after measurable concentrations will be set to zero.
- e. For the calculation of summary statistics of plasma PK parameters, all NR (not reported) and NC (not calculable) values in a data series will be set to missing.

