- f. The specific reasons for 'not calculable (NC)' and 'not reported (NR)' for PK parameters will be provided as footnotes in the PK results listings and summaries.

For vitreous concentration-time data/profiles the following will be applied:

- a. Concentrations that are below limit of quantification (BLQ) prior to the dosing (Pre-dose) will be set equal to zero. Post dose BLQ concentrations will be set to zero.
- b. Where there are no results, these will be set to missing.

c. If more than 75% of values per nominal timepoint and treatment group are BLQ, then all descriptive statistics, except for nBLQ, will be denoted as not calculable (NC).

Conversion of categorical values

In some instances, continuous variables are expressed as a range (i.e., < 10). In such cases, values may be converted to the range boundary (upper or lower limit as applicable). As an example, a value of <10 may be converted to 10. Such substitutions will be clearly documented in the footnotes of relevant outputs.

Coding of Events and Medications

Medical history and AE verbatim terms will be coded using the Medical Dictionary for Regulatory Activities (MedDRA) using version 23.0. Terms will be coded to the full MedDRA hierarchy, but the system organ class (SOC) and preferred terms (PT) will be of primary interest for the analysis.

Prior and concomitant medications will be coded using the World Health Organization Drug Dictionary using the latest version available at the time of study commencement. Medications will be mapped to the full WHO-DD Anatomical Therapeutic Chemical (ATC) class hierarchy, but PTs will be of primary interest in this analysis.

Treatment Groups

- Cohort 1 ONL1204 25 μg
- Cohort 2: ONL1204 50 µg
- Cohort 3 ONL1204 100 μg
- Cohort 4 ONL1204 200 μg
- Overall

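### Plasma BLQ values: the SAP sets them to zero but still asks for geometric statistics, dropping the protocol's set-to-missing rule, and at 4 patients per cohort its suppression rule acts only when all 4 are BLQ

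*SAP*

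**What the plan says.** **Imputation.** SAP section 3 (Handling of Missing Data, plasma rule a) states: "Post dose BLQ concentrations will be set to zero". Pre-dose BLQ values are also zero.

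**Statistics required.** SAP section 3 (General Considerations, PK data) lists n, number BLQ, mean, SD, median, minimum, maximum and CV% for concentrations, and adds that "geometric mean and geometric coefficient of variation (geo CV%) values will be presented". It gives no separate BLQ rule for the two geometric statistics.

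**Safeguard.** Plasma rule c says: "If more than 75% of values per nominal timepoint and treatment group are BLQ, then all descriptive statistics, except for nBLQ" are to be marked not calculable (NC).

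**Protocol.** Section 9.3.1.7 (Systemic PK) also uses zero for descriptive statistics, but makes an exception: "For the calculation of geometric mean and geometric CV%, all BQL values will be set to missing". SAP section 15, on changes to the planned analysis, is marked not applicable.

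**Cohort size.** Protocol 4.1: "Sixteen patients will be enrolled in 4 ascending dose groups". The text under the study schematic gives the number per cohort: "After all 4 patients in a cohort have completed Visit 5". Protocol 4.2.2 lets the safety review committee delay the next cohort "or to enrol additional patients in the current cohort if safety concerns are identified". The SAP's treatment groups are the four cohorts and Overall.

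**The concern.** There are two separate problems.

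First, a geometric mean is built from logarithms, and a zero has none. The protocol avoids this with its exception. The SAP keeps the zero imputation and the geometric statistics but not the exception. Programmers could print 0, NC or the protocol's value in the same cell, and each could cite a governing document.

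Second, a suppression rule is needed most at time points that mix BLQ and measured values. In a 4-patient cohort this rule lets every mixed cell through, including one where three of the four inputs are imputed.

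Plasma Table 14.2.1 is affected. Protocol 1.3.2 intends these data to confirm that drug is not detected in plasma, so that systemic PK need not be evaluated in later studies. A table that speaks to that decision should not print figures set by the imputation.

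**Working it through.** The plan derives no figure here, so there is none to reproduce. The inputs are the rules above, 4 patients per cohort (16 in 4 groups), and the sample SD with divisor n − 1.

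**A. Geometric statistics**

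Geometric mean = exp[(1/n) Σ ln xᵢ]; geometric CV% = 100 × √[exp(s²) − 1], where s is the SD of ln xᵢ.

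| Cell of 4 | SAP (BLQ = 0) | Protocol 9.3.1.7 (BLQ = missing) |
|---|---|---|
| 1 BLQ: 0, x, y, z | ln 0 undefined; product form gives 0; geometric CV% undefined | (xyz)^(1/3); geometric CV% from 3 values |
| 3 BLQ: 0, 0, 0, x | same | x, from one patient; geometric CV% not estimable |

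The conflict starts at one BLQ value and does not depend on the 75% threshold.

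**B. When the safeguard acts**

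Smallest number BLQ, k, that satisfies each condition:

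| n | k/n > 75% (SAP) | k/n ≥ 75% |
|---|---|---|
| 3 | 3 | 3 |
| 4 | 4 | 3 |
| 5 | 4 | 4 |
| 16 (Overall) | 13 | 12 |

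At n = 4, 3/4 = 75.0%, which is not more than 75%. At n = 5, 4/5 = 80%. At n = 16, 13/16 = 81.25%. For any n of 4 or fewer, the SAP rule acts only when every value is BLQ.

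**C. What is printed at 3 of 4 BLQ, with one measured value x**

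- Mean = (0 + 0 + 0 + x)/4 = x/4.
- Sum of squares = 3(x/4)² + (3x/4)² = 12x²/16 = 3x²/4. Variance = (3x²/4)/3 = x²/4, so SD = x/2.
- CV = (x/2)/(x/4) = 200%, whatever x is.
- Median = 0, minimum = 0, maximum = x.

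The mean is below the limit of quantification whenever x is less than 4 times that limit. The documents give a limit only for the rabbit assay (1 ng/mL, Protocol 1.2.1). If the human assay had the same limit, which is an assumption, any x from 1 to just under 4 ng/mL would print a mean below it; x = 1.5 gives 0.375.

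**D. How often**

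The documents give no BLQ probability. If each of 4 patients were independently BLQ with probability p (an assumption):

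| p | P(3 of 4) = 4p³(1 − p) | P(4 of 4) = p⁴ |
|---|---|---|
| 0.50 | 0.25 | 0.06 |
| 0.75 | 0.42 | 0.32 |
| 0.90 | 0.29 | 0.66 |
| 0.95 | 0.17 | 0.81 |

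Near the sponsor's expectation (p close to 1) the all-BLQ cell dominates, and there the SAP rule works.

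**The case against.** The strongest reply is that little is at stake. PK is an exploratory endpoint and no hypothesis is tested. The number BLQ, the median and the minimum stand beside the mean, and individual concentrations are listed. Setting BLQ to zero for arithmetic statistics is the protocol's own rule, carried over faithfully, and a suppression threshold is partly a matter of preference. All of this stands and keeps the point minor. It does not answer the geometric statistics, where the SAP departs from the protocol without saying so.

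Four stronger readings are tempting, and the documents do not support them.

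- *Mixed cells are the likely case.* Protocol 1.3.2 expects no detectable plasma drug, which points to all-BLQ cells. Mixed cells are only plausible.
- *The safeguard never acts short of every value being BLQ.* This is true for 4 or fewer evaluable patients. It is false for Overall (13 of 16) and for a cohort enlarged to 5 (4 of 5).
- *Vitreous has the same defect.* The SAP repeats the threshold for vitreous, but SAP 4.1.4.1 admits to the ocular PK population only patients with a quantified vitreous concentration. If that means above the limit, BLQ values do not enter the summary. Protocol 9.3.1.7 concerns plasma, so there is no vitreous rule to restore.
- *The geometric mean cannot exist in this trial.* That holds only for the SAP read alone. Under the protocol it exists, though at 3 of 4 BLQ it rests on one patient.

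The denominator is also open. Plasma summaries use the plasma PK population, which needs a profile giving at least one of Cmax, Tmax or AUC (SAP 4.1.4.2). If that excludes patients who are BLQ throughout, n may fall below 4.

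**Conclusion.** The point holds in two parts.

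The SAP's plasma geometric mean and geometric CV% are wrong as written. From one BLQ value upward they are zero or undefined, they conflict with Protocol 9.3.1.7, and the SAP declares no change. This does not depend on cohort size.

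The threshold is a weaker, separate point. With exactly 4 evaluable patients, a 3-of-4 BLQ cell escapes suppression and prints mean x/4 and a CV of 200% that says nothing about the drug. It assumes the planned cohort size and that such a cell occurs, which is plausible but not shown to be likely.

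Severity is low: the affected output is exploratory and descriptive, and no test depends on it.

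**What to change.** 1. Add to the SAP plasma rules that BLQ values are set to missing for the geometric mean and geometric CV%. Print the n used next to the number BLQ, and show geometric CV% as NC when fewer than 2 values are quantifiable. If the sponsor does intend zeros there, section 15 should say so and define the calculation.
2. In plasma rule c, change the threshold to 75% or more. Keep NC for everything except n and the number BLQ, and also show the maximum when at least one value is quantifiable.

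The second change makes the rule act at 3 of 4 in a planned cohort and at 12 of 16 in Overall; nothing changes at n = 3 or n = 5. A 2-of-4 BLQ cell would still print a mean with half its inputs imputed, as the protocol's zero rule allows. Replacing the percentage with a minimum count of 3 quantifiable values would be worse for Overall: at 13 of 16 BLQ it would print a mean built on 13 zeros where the SAP now prints NC.

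The cost is a few SAP sentences and no new data. Fewer means will be printed for 4-patient cohorts, but individual values remain in Listing 16.2.6.1.

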4. ANALYSIS POPULATIONS

In this study five analysis populations are defined: The Intent-to-Treat (ITT), Safety population, Per Protocol, Pharmacokinetic (PK) and Pharmacodynamic (PD).

Furthermore, any additional exploratory analysis not identified in the SAP will be identified in the final CSR as exploratory post hoc analyses, including analyses for additional study populations or subgroups of interest.

Population Descriptions

4.1.1 ITT Population

The ITT population will be defined as all patients enrolled for the study.

All disposition and demographic data analysis will be based on the ITT population. All listings will be presented by the ITT population.

4.1.2 Safety Population

The Safety population will be defined as all patients who received the study drug and will be based on actual treatment received.

All safety analyses will be based on the Safety population.

4.1.3 **Per Protocol Population**

The per protocol formulation is defined as all patients who received their assigned treatment and includes all those with no major protocol deviations.

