Target Population:	Patients who present between 1 week (7 days) to 4 weeks (28 days) of a macula-off RRD (based on patient-reported history of loss of central vision) for whom standard retinal reattachment surgery by means of a pars plana vitrectomy and gas tamponade is indicated.

Number of	Approximately 16 patients will be enrolled in this study.								
Patients:	• 4 ascending dose groups; 4 active. The first patient in each dose group will be observed for at least 14 days post-surgery (through visit 6) prior to enrolling the remainder of the patients in that dose group.								
	• Patients may be replaced who do not receive an injection of study medication, or for discontinuing from the study for reasons unrelated to treatment before completing Visit 4. All patients receiving injection of study drug will be followed for safety and tolerability.								
Study Visits	There is a minimum of 8 scheduled study visits:								
	• Visit 1: Day 1 (baseline/drug injection)								
	• Visit 2: Day 2 (1 day post-injection*)								
	• Visit 3: Day of Vitrectomy (3 + days post-injection in accordance with standard of care vitrectomy)								
	• Visit 4: Postoperative visit (1 day post-surgery)								
	• Visit 5: Post-operative visit (2 weeks post-surgery and clearance of sentinel patient/cohort (14 days +4 days post-surgery))								
	• Visit 6: Week 6 (±7 days)								
	• Visit 7: Week 9 (±7 days)								
	• Visit 8: Week 24/Exit (±14 days)								
	*additional visits between visit 2 and 3 per investigator's discretion								
Objectives:	To evaluate safety and tolerability of a single intravitreal injection of ONL1204 in patients with macula-off, RRD.								
Study Design:	This is a single-injection, open-label dose escalation study.								
Primary Objective:	The primary objective will be to determine the Maximum Tolerated Dose (MTD) of ONL1204 and select doses for Phase 2. Determination of this will be through review of the parameters measured in the Schedule of Assessments, as well as adverse event (AE) reports.								

Page 6 of 52

Exploratory Objective: During the study, ocular fluid samples will be collected at the time of study drug injection and at the time of vitrectomy. These samples will be used for pharmacokinetic and pharmacodynamic analyses, the results of which will help inform the dose selection for the Phase 2 trial(s).

Page 7 of 52

STUDY SCHEMATIC

Figure 1 Study Schematic

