8.2 Adverse Event Definition

AE means any untoward medical occurrence in a patient or subject administered a pharmaceutical product or undergoing a study procedure; the untoward medical occurrence does not necessarily have a causal relationship with this treatment. An AE can therefore be any unfavorable and unintended sign (including an abnormal laboratory finding), symptom, or disease temporally associated with the use of a medicinal (investigational) product or study procedure whether or not it is related to the medicinal product or study procedure. This includes any newly occurring event, or a previous condition that has increased in severity or frequency since the administration of study drug or study procedure.

Page 38 of 52

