9.1.2 Sample Size

The number of patients to be enrolled has been selected to provide information for this Phase 1 study. No formal sample size calculation is provided given the pilot nature of this study.

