9.1.3 Analysis Populations

9.1.3.1 ITT population

All patients will be included in the intent to treat ITT Population.

Safety Population: All patients will be included in the Safety Population. Patient data will be summarized according to the dose they received.

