- Baseline: The baseline value is defined as the last available valid (quantifiable continuous or categorical value), non-missing observation for each participant prior to first study drug administration. Repeat and unscheduled assessments will be included in the derivation of the baseline values.
- Change from Baseline: The change from baseline value is defined as the difference between the result collected/derived at a post-baseline visit/time point and the baseline value.

The change from baseline value at each post-baseline visit/time point will be calculated for all continuous parameters using the following formula:

Change from Baseline Value = Result at Visit/Time Point – Baseline Value

The change from baseline value will only be calculated if the specific post-baseline visit/time point result and the baseline value for the parameter are both available and will be treated as missing otherwise.

• Study day: The study day of an event is defined as the relative day of the event starting with the date of the first study drug administration (reference date) as Day 1 (there will be no Day 0).

The study day of events occurring before the first study drug administration will be calculated as:

Study Day = (Date of Event - Date of First Study Drug Administration)

For events occurring on or after Day 1, study day will be calculated as:

Study Day = (Date of Event - Date of First Study Drug Administration) + 1

Study days will only be calculated for events with complete dates and will be undefined for events that are 'Ongoing' at the end of the study.

Relative days compared to an alternative reference point will be calculated similarly, but the alternative starting reference start date will be used instead of the date of the first study drug dosing.

- Prior Medications: Prior medications are defined as any medication where the use was stopped prior to the first administration of the study medication.
- Concomitant Medications: Concomitant medications are defined as any medication (other than the study drug) that was used at least once after the first administration of the study drug. Medications that were stopped on the same date as the first study drug administration will be defined as concomitant medications. If a clear determination cannot be made (partial medication end dates) the medication will be classified as concomitant.

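### Adverse events starting between the vitreous tap and the injection, or in a patient tapped but never injected, cannot reach any adverse event summary table, including the relationship-to-procedure tables

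*SAP*

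**What the plan says.** **Sequence.** Protocol 4.1 has eligible, consented patients come to Day 1, when "patients will undergo a vitreous tap for cytokine and other potential molecular biomarker analysis followed by a single intravitreal injection of ONL1204". Table 4-1 enters the tap in the pre-injection column, and the SAP's design text and section 11 give the same order. Protocol 6.4.2 alone describes the baseline tap as post-injection.

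**Purpose and risk.** The tap supplies a biomarker sample (Protocol 1.3.3). Protocol 1.4.3 lists infection, bleeding, raised pressure, retinal tears and loss of the eye among the risks of tap and injection.

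**What counts as an adverse event.** Protocol 8.2 covers "any untoward medical occurrence in a patient or subject administered a pharmaceutical product or undergoing a study procedure". Protocol 8.1 closes the pretreatment period at the first study medication or study procedure, so an event after the tap is no longer a pretreatment event.

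**Who is in the safety set.** Protocol 9.1.3.1: "All patients will be included in the Safety Population", with data summarised by dose received. SAP 4.1.2: "The Safety population will be defined as all patients who received the study drug and will be based on actual treatment received".

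**Which events are tabulated.** SAP 13.1.1 confines adverse event summaries to treatment-emergent events, and SAP 3 (Key Definitions) starts these at first drug administration. SAP 18 puts every table in the 14.3.3 series on the Safety Population.

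**Which events are listed.** SAP 4.1.1 and the index in SAP 19 (listings 16.2.7.1 to 16.2.7.4) use ITT. SAP 13.1.1 says the listings use the Safety Population.

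**Declared changes.** SAP 15 reports none.

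**The concern.** Safety is the primary endpoint (Protocol 3.1), and the protocol sets out to measure harm from procedures as well as from drug: Protocol 9.3.1.1 plans separate causality analyses for study-eye events by drug and by procedure. The tap is an invasive study procedure that comes before the drug. Yet the tables meant to show procedure harm are built so that they can show only harm that begins after the drug, in patients who received it.

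A reader of the study report would take a zero in table 14.3.3.6 to mean that no procedure-related event occurred. Under the SAP it could equally mean that the event came before the injection, or that the patient was never injected. With four patients per cohort, one such case is the difference between no events and an event.

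**Working it through.** There is no planned figure to reproduce: Protocol 9.1.2 states "No formal sample size calculation is provided given the pilot nature of this study". The check traces the definitions and then adds simple arithmetic for scale.

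**Two conditions must both be met to enter an adverse event table:** the patient is in the SAP Safety Population (received drug), and the event is treatment-emergent (after first drug).

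1. *Patient tapped, event begins, then injected.* The population condition is met. The event condition fails, because onset precedes the drug. If the event later worsens, Protocol 9.3.1.1 would count it, since its definition includes worsening. The SAP definition leaves worsening out, so the event stays out unless it is recorded again as a new event. The SAP's missing-date rules class an event with no dates, or with only a month and year matching the injection, as treatment-emergent. The loss therefore concerns events whose onset is recorded as before the injection.
2. *Patient tapped, event begins, injection withheld.* Both conditions fail: no drug was received, and there is no first administration to count from. The treatment groups in SAP 3 are four doses and an overall column, so there is also no column for this patient. The patient would appear in disposition table 14.1.1, which is on ITT (assuming a tapped patient counts as enrolled), but the event would not be tabulated.
3. *Widening only the population.* Patient 2 now enters the set, but the event is still not treatment-emergent, and patient 1 gains nothing. Both conditions have to change.

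**Scale, by illustration.** Inputs: 4 cohorts × 4 = 16 injected patients. Assumption: k patients are tapped, not injected and replaced, and one of them is harmed. The documents give no rate for this.

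| k | Cohort, SAP | Cohort, all tapped | Overall, SAP | Overall, all tapped |
|---|---|---|---|---|
| 1 | 0/4 | 1/5 = 20.0% | 0/16 | 1/17 = 5.9% |
| 2 | 0/4 | 1/6 = 16.7% | 0/16 | 1/18 = 5.6% |
| 3 | 0/4 | 1/7 = 14.3% | 0/16 | 1/19 = 5.3% |

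The exact 95% interval for 1/5 runs from 0.5% to 71.6%, so what matters is whether the event is shown, not the estimated rate.

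**Likelihood.** The only risk figure for the tap is endophthalmitis at 1 in 2000 to 1 in 3000 (Protocol 1.3.3). The chance of at least one case in 16 taps is 1 − (1 − 1/2000)^16 = 0.80%, or 1 − (1 − 1/3000)^16 = 0.53%. The other listed harms have no stated rate.

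**The case against.** A safety set of treated patients is conventional, and the objective is the maximum tolerated dose of ONL1204 (Protocol 2.1). Protocol 9.1.3.1 goes on to summarise by dose received, the schematic text says "16 patients will be enrolled and treated, starting with the lowest dose, Cohort 1", and Protocol 6.2 has every patient receiving drug, so all patients may simply have meant all treated patients. Protocol 9.3.1.1 itself starts treatment-emergent events at the drug. In an open-label study of 16 patients with no hypothesis test, the listings will be read line by line, and the listing index keeps them on ITT.

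Much of this stands. It is a good reason to keep dose columns by dose received and a drug-anchored definition for the drug tables, and it means the event start point is not the SAP's invention. It does not explain why tables on relationship to procedure should exclude the procedure that precedes the drug. Nor does it settle the listings, since SAP 13.1.1 contradicts the index.

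Two stronger readings are tempting and are not supported.

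- *That harmed, uninjected patients go unfollowed.* The Study Summary says "All patients receiving injection of study drug will be followed for safety and tolerability" and lets uninjected patients be replaced. But Protocol 8.6 monitors all adverse events to exit, 8.9 requires serious events to be reported from consent whatever the cause, and 6.8 asks for exit assessments on discontinuation. The sentence needs reconciling with these; it does not show that follow-up is absent.
- *That a post-tap reading becomes baseline and distorts dose escalation.* The SAP takes the last value before drug and adds that "Repeat and unscheduled assessments will be included in the derivation of the baseline values". No reading between tap and injection can be shown to be planned. The dose-limiting pressure criterion is absolute (above 30 mmHg for 3 consecutive days), and Protocol 10.2 does not name pressure change from baseline among the review committee's inputs. Nothing shows that the committee uses the SAP's baseline for the inflammation criterion. A pre-tap baseline would also mix tap effects into apparent drug change, so it is a trade-off rather than a correction.

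**Conclusion.** The point holds for the adverse event summary tables. As written, the SAP cannot tabulate an event recorded as starting between tap and injection, or any event in a tapped but uninjected patient. The population part is an undeclared narrowing of Protocol 9.1.3.1. The event part is at odds with Protocol 8.1 and 8.2 and defeats the purpose of tables 14.3.3.6 and 14.3.3.6a.

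The size is small in expectation and large if it happens: 0/4 instead of 1/5 in a cohort for a single case. That figure assumes a tap complication, a withheld injection and a replacement.

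The conclusion rests on the tap preceding the injection, as in Protocol 4.1, Table 4-1 and SAP 11. If the post-injection wording of Protocol 6.4.2 governed, every tapped patient would already have received drug and the gap would close. It would be wrong to infer that the events vanish from the trial record, or that the patients left out are known to be those most likely to be harmed.

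**What to change.** 1. **SAP 4.1.2.** Define the Safety Population, or a procedure-safety set used for tables 14.3.3.6 and 14.3.3.6a, as all patients who had the vitreous tap or received ONL1204. Show tapped but uninjected patients in a separate column and keep the dose columns by dose received.
2. **SAP 13.1.1, tables.** In the relationship-to-procedure tables, count adverse events from the start of the tap. Keep the drug-anchored definition for the other tables.
3. **SAP 13.1.1, listings, and SAP 15.** Set the adverse event listings to ITT, matching SAP 4.1.1 and SAP 19. Record the difference from Protocol 9.1.3.1 in SAP 15.
4. **Protocol.** Reconcile the Study Summary's follow-up sentence with 8.2, 8.6 and 8.9, and the tap timing in 6.4.2 with 4.1 and Table 4-1.

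The cost is some wording, one extra column that will probably be empty, and a second adverse event start point that needs a footnote so the two sets of tables are not compared directly.
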